9.3.2 Regulatory Reporting for Studies Conducted Under DMID-Sponsored IND

NA

9.3.3 Regulatory Reporting for Studies Not Conducted Under DMID-Sponsored IND

NA

9.3.4 Other Adverse Events (if applicable)

NA

9.3.5 Reporting of Pregnancy

Participant population is pediatric and not prone to pregnancy.

9.4 Type and Duration of Follow-up of Subjects after Adverse Events

AEs will be followed until resolution even if this extends beyond the study-reporting period. Resolution of an AE is defined as the return to pretreatment status or stabilization of the condition with the expectation that it will remain chronic. CM is a disease with a high burden of long-term neurological deficits²⁵⁸. Participants will all be asked to return to clinic at 1, 3, 6 and 12 months (± 2 weeks) post-randomization for evaluation of recovery; the 12-month (± 2 weeks) visit will serve as the final study visit.

9.5 Halting Rules

The following eventuality would trigger temporary suspension of enrollment until a safety review is convened and further evaluation undertaken:

- Five subjects where current HPS regimen is unable to achieve the target Na⁺ levels of 150-160 mmol/L.
- Any SAE deemed to be related to each of the experimental medical interventions (ventilator support or infusion of 3% hypertonic saline solution).

DMID retains the authority to suspend additional enrollment and study interventions during the entire study, as applicable.

9.6 Safety Oversight (ISM plus SMC or DSMB)

Safety oversight will be under the direction of a DSMB composed of a pediatrician, a pediatric intensivist, a statistician, and others at the discretion of NIAID. The DSMB will meet annually to assess safety and efficacy data on each arm of the study. The DSMB will review aggregate safety data for increased rate of occurrence of serious unexpected adverse reactions. If halting rules are initiated, more frequent meetings may be held. The DMSB will operate under the rules of a DMID-approved charter that will be written at the organizational meeting of the DSMB. At this time, each data element that the DSMB needs to assess will be clearly defined. The DSMB will advise DMID of its findings.

10 CLINICAL MONITORING

10.1 Site Monitoring Plan

Site monitors from the Research Support Centre at the University of Malawi College of Medicine will visit the clinical research site to review the individual subject records, including consent forms, CRFs, supporting data, laboratory specimen records, and medical records (physicians' progress notes, nurses' notes, participants' hospital charts), to ensure protection of study subjects, compliance with the protocol, and accuracy and completeness of records. The monitors also will inspect sites' regulatory files to ensure that regulatory requirements are being followed and sites' pharmacies to review product storage and management.

11 STATISTICAL CONSIDERATIONS

11.1 General Design and Objectives

We propose a single site randomized controlled trial (RCT) of two adjunctive therapeutic approaches compared to usual care (UC) in treating increased brain volume in Malawian children with CM and MRI-supported evidence of severely increased brain volume. Children will be randomized to one three arms: Arm 1: UC plus immediate ventilator support (VENT), Arm 2: UC plus hypertonic saline (HPS), Arm 3: UC. Arm 2 and Arm 3 would receive rescue ventilation in the event of a respiratory arrest.

11.2 Stratification and Randomization

Stratification by retinopathy status (negative/positive) is necessary as the mortality rates vary between children of varying retinopathy status. For this study, stratification by gender or age is not necessary.

11.3 Testing the adequacy of randomization

Prior to analysis, the adequacy of the randomization will be evaluated by comparing all baseline characteristics of the three study arms. These variables include characteristics such as age, gender, weight, malarial retinopathy status, height and duration of symptoms prior to admission. Where substantive differences exist in these variables, they may be controlled for in subsequent analyses by regression techniques. The degree of similarity between the study arms will be tested using, as appropriate, ANOVA, nonparametric tests and chi-square tests. However, following Altman²⁵⁹, we will be guided by the degree of dissimilarity rather than strict statistical significance.

11.4 Outcomes

The primary endpoint is death within one week following randomization. In Arm 2 and Arm 3, the endpoint will include failure of the initial treatment allocation such that the patient requires rescue ventilation. Several secondary outcomes will be assessed in the trial. Table 8 gives a brief description and preferred analytic strategies. Additional details are provided elsewhere in the Protocol.

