 - a. Given these successes and challenges and the potential beneficial effects on mortality described in Section 11.2, a study comparing two interventions to Usual Care that will answer our original research questions prior to study closure will be challenging but remains feasible. Answering the question whether mechanical ventilation or intravenous hypertonic saline decreases mortality risk in children with CM requires sing participants enrolled in the BMP observational study prior to clinical trial commencement as Historical Controls (obviating the need for randomizing high numbers of participants into the Usual Care arm)

Historical Controls:

We identified potential Historical Controls from the electronic database of the completed observational study of cerebral malaria pathogenesis. In order to minimize temporal differences between participants randomized in the clinical trial, we began our search with children enrolled in the observational study in 2017 and moved backwards in time.

Neuroradiologists affiliated with the Treating Brain Swelling clinical trial assessed the brain MRI scans on over 200 children enrolled in the observational study. These images dated from 2014-2017.

Once consensus brain volume scores on these MRI scans were assigned by the neuroradiologists, we retrieved demographic and clinical data on children who had assigned brain volume scores of 6-8 from the master Blantyre Malaria Project database. Demographic, clinical, and outcome data were compared between children enrolled in the observational study who had brain volume scores of 6-8, and children randomized in the Treating Brain Swelling clinical trial and were randomized to Usual Care with the same range of brain volume scores. Comparisons were made between the following variables: age (in months), sex, Blantyre coma score, admission glucose, admission hematocrit, admission platelet count, and outcome. Statistical analysis: Comparisons between groups were made using t-tests or Wilcoxon test (continuous variables), ANOVA (categorical variables), or chi squared tests (dichotomous variables), as appropriate.

We found no difference in the variables in question between children enrolled in the observational study who had MRI brain volume scores of 6-8, and participants randomized in the clinical trial who had MRI brain volume scores of 6-8.

Table 4. Continuous variables compared between historical controls and randomized study participants

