Variable	OS mean	OS SD	TBS mean	TBS SD	P value
Age (months)	48.25	27.54	59.63	27.88	0.168
Glucose	5.87	2.94	5.63	3.13	0.914 ^d
Hematocrit (%)	23.36 ^a	6.29	25.54	6.97	0.555 ^d
Platelets (*1000/MicroL)	148.9 ^b	373.7	94.3 ^c	176.2	0.993 ^d

OS= observational study (n=48), SD= standard deviation, TBS= treating brain swelling clinical trial (n=16)

^a n=45, ^b n=47, ^c n=15. ^d nonparametric test.

There was no significant difference in admission Blantyre Coma score (p=0.948), sex (p=0.885) or outcome (death/survival, p=0.551) between the 48 children in the observational study and the 16 randomized participants in the Treating Brain Swelling clinical trial.

We therefore conclude that participants enrolled in the observational study (n=48) are comparable to participants randomized to Usual Care (n=16) in the Treating Brain Swelling clinical trial.

We anticipate enrollment in the Usual Care arm in the 2023 season (see below) at a reduced ratio compared to the intervention arms.

Possible future declaration of futility of the ventilation arm:

If we combine the mortality risk in Historical Controls and participants already randomized to Usual Care, the mortality risk of the combined historical control group and children randomized to Usual Care is 36%. At the end of the 2021 season, the mortality risk in the VENT arm was 26.3%. (Five of 19 participants randomized to VENT died or were brain dead.) With only these data, the test of the null hypothesis of a null difference in mortality is not significant (p-value 0.818, 2-sided test).

We believe it likely that VENT will, in the future, be declared futile. If so, randomization of participants enrolled in the Treating Brain Swelling clinical trial after the declaration of futility of VENT would be to HPS or UC. A formal approach to futility assessment for VENT is provided below.

Table 4. Projected enrollment

	2018 – 2021	2022	2023	Total
*Usual care (UC)	64	0	4	68
Ventilatory support (VENT)	19	7	6	32
Hypertonic saline (HPS)	3	14	15	32

*historical controls + study participants enrolled in 2018 and 2019.

Assuming that enrollment in 2023 follows the same trend seen since the beginning of the clinical trial, we will be able to detect a 50% or more risk reduction in either the VENT or HPS arms, compared to UC.

Choice of interventions

The three study arms of the study will be:

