5.3 Treatment Assignment Procedures

5.3.1 Randomization Procedures

The study will be randomized, but not blinded. Participants will be randomized after completing the eligibility screening procedures. A block randomization scheme will be used to ensure groups of equal size. Blocks sizes of six and nine will be rotated to decrease the predictability of group allocation within a block for data collectors. Children with retinopathy-positive CM will be randomized separately from those with retinopathy-negative CM.

Randomization is based on obtaining a consensus interpretation of brain volume per MRI. If this is not possible for any reason, study participants will be screened but not randomized, and will remain on the PRW. All other study procedures will be followed as described in this protocol.

Randomization is predicated on the risks and benefits as described in this protocol. Endotracheal intubation is required for participants randomized to the “intubation + mechanical ventilation” arm. The current coronavirus pandemic affects the risk/benefit ratio of this arm of the study because endotracheal intubation increases the risk of aerosol spread of the coronavirus (US CDC COVID19 guidance, 4.4.20, www.cdc.gov/coronavirus/2019-ncov/hcp/guidance-risk-assesment-hcp.html). Randomization to the mechanical ventilation arm will be adjusted in accordance with local IRB recommendations during the coronavirus pandemic.

All possible blocks with balanced combinations of group assignment will be documented. Next computer-generated random numbers will be used to select from the balanced blocks. Assignment of study subjects to randomization arm will be performed electronically, through the online data capture mechanism. If Internet service is unavailable at the time of randomization, back up sequentially numbered opaque sealed envelopes prepared before the trial begins will be available. The envelopes will be stored in a secure location with access limited to key study personnel. After a caregiver provides consent for a patient to participate in the study, study arm assignment will first be attempted electronically. If Internet service is unavailable, study personnel will open the next unopened sequentially numbered envelope to reveal the group assignment and dosing calculation sheet.

A master log of all screened and enrolled subjects will be maintained. A subject is considered randomized upon online assignment or opening the envelope to indicate treatment assignment.

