11.5 Sample Size and Power

For the primary outcome death/failure of the intervention, we conduct two parallel studies: (i) VENT versus control UC, (ii) HPS versus control UC. Approximately 128 children will be enrolled in the studies. This includes the 64 children in UC comprised of 16 randomized to UC in the 2018-2019 malaria seasons and augmented by 48 historical controls from previous seasons (2014-2017). We also randomized 16 children to VENT in the 2018-2019 malaria seasons.

Table 8: Summary of outcome measures and analytic plan		
Outcome measure	Outcome type/scale	Analytic method
PRIMARY OUTCOME		
Success of primary intervention or survival in the first 7 days after randomization	Binary	Logistic regression
SECONDARY OUTCOMES		
Brain volume determination (MRI on admission, then daily)	Ordinal	Ordinal regression
Optic Nerve Sheath Diameter (on admission, then daily)	Continuous	Linear regression. Serial assessments by repeated measures analysis
Transcranial Doppler ultrasound (on admission, then daily)	Continuous	Linear regression. Serial assessments by repeated measures analysis
Opening CSF pressure (mm CSF) (on admission)	Continuous	Linear regression
Heart rate variability patterns	Continuous	Linear regression. Serial assessments by repeated measures analysis
Neurologic exam * (on admission, then twice daily)	21 binary and 5 continuous variables	Linear or logistic regression
Papilledema (on admission, then daily)	Binary	Logistic regression
Severe neurologic sequelae at 16 and 12 months	Binary	Logistic regression. Serial assessments by repeated measures analysis
Hypotension that occurs within 30 minutes of sedation administration, initiation of mechanical ventilation or ventilator pressure adjustment.	Binary	Logistic regression.

Since the beginning of this study, we faced several logistical challenges but had success in recruiting 32 children in 2018-2019 (16 each in VENT and UC). Based on our current data, the estimated mortality in UC and VENT are respectively, 36% and 25%. Maintaining the mortality rate in UC, a one-sample lower test at significance level $\alpha=0.05$ of a null difference has 80% power to detect a reduction in mortality to 18% in VENT with 33 subjects in VENT.

[figure not shown]

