11.6 Interim Analyses

The TBS design is a 4-stage sequential plan to compare VENT to UC on the outcome of mortality. Based on historical controls and initial randomization to UC before 2020, mortality is

assumed fixed at $p_0 = 0.28$. We test the hypothesis that mortality p in VENT is lower, i.e., we test $H_0 : p = p_0$ versus $H_1 : p < p_0$ at significance level $\alpha = .05$. VENT will be declared superior to UC, if we can demonstrate a relative risk reduction of 50% with 80% power. This needs a sample of 38 subjects.

Boundaries for the 4-stage plan are derived from the power family. Early stopping is to reject the null hypothesis. Our first interim analysis was conducted with data from the 2019-2020 malaria seasons. Observed mortality in VENT was 12.5% (2/16). The conclusion was to continue to the next stage. Our current estimate, at the end of the 2021 season is 15.8% (3/19). In accordance with the design, we must continue to the next stage (i.e., 2022 season). The revised boundary information is depicted in the figure.

Figure: Boundary plot at conclusion of stage 2

Legend: The scale is the maximum likelihood estimate (MLE) of the mortality difference (PDIFF), $\theta = p - p_0$ against the actual information level. At stage 1, observed $\theta = 0.125 - 0.28 = -0.155$, and at stage 2, $\theta = 0.158 - 0.28 = -0.122$. The rejection boundaries are not crossed.

Conditional power and predictive power

Conditional power (CP) is the power to reject the null hypothesis $H_0: \theta = 0$ at all future stages given the cumulative interim data. This calculation shows: (a) at the current estimated difference in mortality $\theta = -0.122$, CP=76.1%, (b) at zero difference in mortality, CP=18.6%, (c) at the hypothesized difference, $\theta = -0.14$, CP=82.9%. Predictive power (PP) is the posterior probability

of rejecting the null at the next stage given the current data, assuming a non-informative prior on the mortality difference. PP=66.1% at the current stage.

Based on these assessments it behooves that we proceed to stage 3.

Hypertonic saline (HPS) vs UC

We have our first sample of 3 subjects, one of whom died. Although hardly necessary, a formal analysis provides the exact 95% CI for mortality in HPS, (0.008, 0.906).

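### The 48 historical controls have no stated time zero or 7-day window, so deaths that cannot count in the trial arms may be included in the usual-care benchmark p0

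*Combined protocol and SAP*

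**What the plan says.** **Trial children.** Section 11.4: "The primary endpoint is death within one week following randomization". Section 5.3.1 fixes when that clock starts: "Participants will be randomized after completing the eligibility screening procedures", and "A subject is considered randomized upon online assignment or opening the envelope to indicate treatment assignment". Between the MRI and that moment lie the real-time reading of the scan and a separate consent for randomisation (Sections 7.2, 8.1 and 14.4). Section 2.3 says that one neuroradiologist read scans in real time in 2018. From 2019 two independent reads were required, both with a score of at least 6.

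**Historical controls.** Section 4 describes children in a completed observational study whose 2014-2017 scans were scored retrospectively: "we retrieved demographic and clinical data on children who had assigned brain volume scores of 6-8 from the master Blantyre Malaria Project database". Their outcome appears only in the comparability check, as "outcome (death/survival, p=0.551". No time origin or follow-up window is attached to it.

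**Use of the controls.** Section 11.5 describes the "64 children in UC comprised of 16 randomized to UC in the 2018-2019 malaria seasons and augmented by 48 historical controls from previous seasons". Section 11.6 then sets the null value: "Based on historical controls and initial randomization to UC before 2020, mortality is" taken as fixed at p0 = 0.28. The VENT test compares against that constant, and Section 11.5 makes UC the comparator for HPS as well.

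**The concern.** A child who qualifies on MRI but dies before assignment never enters a trial arm. A historical child with the same course is in the control group and counts as a death. The interval between MRI and assignment is time that trial children must survive to be counted, and nothing in the plan imposes the same condition on controls. The 7-day limit raises a similar question: it is explicit for trial children and unstated for controls.

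Both differences act in one direction on the count of deaths: they can add control deaths but cannot add VENT or HPS deaths. They are separate from whether the children resemble each other at admission, so the comparability check in Section 4 and the regression adjustment in Section 11.3 do not address them. Because p0 enters the VENT test as a constant, any excess in it appears as treatment benefit point for point.

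**Working it through.** **1. Inputs.** From Section 11.6: p0 = 0.28, target 0.14, one-sided alpha 0.05, power 80%, N = 38, VENT at stage 2 = 3/19. From Section 11.5: 48 + 16 = 64 UC children, so 48/64 = 75% are historical. Not in the documents: the MRI-to-randomisation interval, control death times, and the number of control deaths in the gap (k). I therefore assume k and show a range.

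**2. Reproducing the plan's figure.** One-sample normal approximation with variance under the alternative: n = (1.645 + 0.842)² × 0.14 × 0.86 / (0.28 − 0.14)² = 37.98, so 38. The stated N is a fixed-sample figure that depends directly on p0.

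**3. Rejection rule at n = 38, single look.** 0.28 − 1.645 × √(0.28 × 0.72 / 38) = 0.160, and 0.160 × 38 ≈ 6.1. The test rejects at 6 deaths or fewer. This simplifies the 4-stage plan, whose boundary shape is not stated.

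**4. Effect of k gap deaths.** 0.28 × 64 is about 18 deaths (inferred). A landmark removes k children from numerator and denominator, giving (18 − k)/(64 − k). If VENT does nothing, its true rate is taken to be the aligned rate, and the false-positive probability is the binomial P(X ≤ 6 | n = 38).

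| k (assumed) | aligned control rate | P(ineffective VENT passes) |
|---|---|---|
| 0 | 0.28 (18/64 = 0.281) | 0.062 at 0.28 |
| 1 | 17/63 = 0.270 | 0.080 |
| 2 | 16/62 = 0.258 | 0.106 |
| 3 | 15/61 = 0.246 | 0.140 |
| 4 | 14/60 = 0.233 | 0.184 |

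Each gap death lowers the benchmark by a little over one percentage point. At k = 3 the stage-2 difference shrinks from 0.158 − 0.28 = −0.122 to 0.158 − 0.246 = −0.088.

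**5. The other benchmark.** Sections 4 and 11.5 give UC mortality as 36%, about 23/64, with 33 children in VENT. The cut-off is 0.36 − 1.645 × √(0.36 × 0.64 / 33) = 0.223, so the test rejects at 7 deaths or fewer. For k = 0 to 4 the rate (23 − k)/(64 − k) is 0.359, 0.349, 0.339, 0.328 and 0.317, and the false-positive probability is 0.053, 0.067, 0.085, 0.107 and 0.133. The inflation is smaller. The conflict between 0.28 and 0.36 is a separate matter that the sponsor must resolve.

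**6. Deaths after day 7.** A control who died late stays in the denominator and becomes a non-event, so each such death would lower the benchmark by 1/64 = 1.6 percentage points. The documents give no count. Few are likely, since Section 2.3 reports that 85% of children have died or been discharged by 72 hours.

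**The case against.** The strongest reply is that the direction is not proven. A reader might infer that p0 **is** inflated. The documents do not show that: the gap may be short (Section 8.3.2 has two radiologists on call at all times), and no control may have died in it. That limit stands.

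A reader might also take the 72-hour figure in Section 2.3 as evidence that early deaths dominate. It is not, because it pools deaths with discharges. The same section says that 63% of the high-risk subset survive, nearly all discharged within that time. The figure shows that hours matter but does not locate the deaths.

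Nor do controls enter on the MRI score alone. They were enrolled in an observational study and scanned, so they too survived to MRI. The two-read step did not apply to the 8 children randomised in 2018, although the second consent did.

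Early recovery could work the other way. If controls who recovered before the index time were also dropped, the shift could vanish: removing 2 deaths and 5 recoverers gives 16/57 = 28.1%, and removing 3 and 8 gives 15/53 = 28.3%. But Section 5.1 lists only the MRI score and willingness to return as randomisation criteria. Unless a coma-score condition was applied to trial children at randomisation, dropping recovered controls has no counterpart in the trial.

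Finally, the 16 randomised UC children passed the trial's own steps, and their outcome did not differ detectably from that of the 48 (p = 0.551). This is relevant but weak: at a rate of 0.28 the 95% half-width for the difference is 1.96 × √(0.28 × 0.72 × (1/48 + 1/16)) = 0.254, about 25 percentage points. It cannot exclude a shift of 1 to 5 points.

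**Conclusion.** The gap in the plan is real. The trial endpoint is anchored to randomisation, and three quarters of the benchmark has no stated anchor, survival condition or window. The bias is conditional. With no control deaths between MRI and a randomisation-equivalent time and none after day 7, there is none. With 1 to 4 gap deaths (assumed), the nominal 0.05 test would pass an ineffective VENT with probability 0.08 to 0.18, against 0.06 without the mismatch; on the 36% base the range is 0.07 to 0.13, against 0.05. These figures rest on an inferred death count, a single-look test and an assumed k.

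The documents are silent on the 7-day window for controls. That silence does not establish that none was applied, because the death/survival variable is reported only in a comparability check. The finding supports stating the time origin and testing its effect. It does not support a claim that the benchmark is known to be too high, nor replacing p0 after two looks have been taken against it.

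**What to change.** **In Section 11.4**, define time zero as randomisation for trial children. For each historical control, define it as MRI time plus the median MRI-to-randomisation interval of the randomised children. Exclude controls who died before that time and count only deaths within 7 days after it. Do not exclude on coma score unless the same condition applied to trial children at randomisation.

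**In Sections 11.6 and 11.7**, keep the fixed p0 = 0.28 test and add a pre-specified sensitivity analysis. Re-estimate p0 and the VENT and HPS comparisons on the aligned set, using the 25th, 50th and 75th percentile intervals. State that a superiority claim will be read together with this result. Substituting a new p0 in the test itself would change the null after outcomes were seen and would require new boundaries and conditional power.

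**Also report** the number of screened children with a score of at least 6 who died before randomisation (the master log in Section 5.3.1 should allow this), and the comparison with the randomised UC children alone.

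**Cost.** MRI and death times must be extracted for 48 existing records. The documents do not say that these times are available for all of them, so the plan needs a rule for missing times. A few controls may be dropped, and the benchmark may become less favourable. If no control died in the gap or after day 7, the sponsor can say so, and the benchmark is stronger for it.
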